1.0 Background

Salt sensitive blood pressure preferentially affects black Americans

Salt sensitive blood pressure (SSBP) is a physiologic phenotype defined by a parallel change in blood pressure in response to dietary salt load. SSBP is fundamentally related to the body's inability to clear salt, leading to elevated blood pressure and a life-long increased risk of cardiovascular disease. SSBP was determined to be an independent risk factor for developing cardiovascular disease in hypertensive patients almost two decades ago¹, and more recently SSBP was found to portend all-cause mortality². It is a prevalent condition that affects up to 50% of normotensive, 75% of hypertensive³, 74% of black American adults⁴, and is estimated to be 6% more prevalent among females than males^{5, 6}. Black Americans are preferentially affected by this phenotype, and represent one of the most at-risk population for cardiovascular diseases related to SSBP. Salt sensitivity is increased with the occurrence of metabolic syndrome associated with abdominal obesity⁷ and insulin resistance⁸. Current tests for SSBP require dietary salt loading, are time-intensive and, more importantly, provide limited mechanistic information on the incompletely characterized mechanisms of tissue salt storage.

Tissue sodium homeostasis is maintained by renal and lymphatic mechanisms

While renal dysfunction is implicated in SSBP⁹, emerging evidence suggests that lymphatic mechanisms additionally regulate tissue salt storage and blood pressure¹⁰ and may contribute significantly to systemic vascular resistance^{11, 12}. The lymphatic system is a central component of the body's circulatory system, functioning in the regulation of tissue sodium homeostasis, in the clearance of high-density lipoproteins¹³ and metabolism of fatty acids⁷. Lymphatic clearance of tissue salt may represent an extra-renal system¹⁴ capable of regulating blood pressure^{15, 16} such that inhibition of this pathway is implicated in salt-sensitive hypertension^{17, 18}. Patients with essential hypertension, who were not evaluated for salt sensitivity, display elevated tissue sodium in peripheral tissues¹⁹. Similar profiles of elevated tissue sodium have been reported in patients with chronic kidney disease²⁰. Additionally, impaired lymphatic clearance and renal dysfunction may also contribute to obesity^{21, 22}, which is an established risk factor for cardiovascular disease. Our overarching hypothesis is that impaired lymphatic and renal vascular function is associated with elevated tissue sodium and fat storage in persons with SSBP.

Magnetic resonance imaging (MRI) tools for measurement of lymphatic and renal function associated with tissue sodium and fat deposition

The critical limitation to interrogating lymphatic and renal clearance of sodium in vivo rests with a lack of noninvasive imaging technologies sensitive to sodium, lymphatic, and renal physiology. To address these limitations, we have recently developed a novel, noninvasive magnetic resonance (MR) lymphangiography technique²³ and applied standardized MRI protocols for measuring tissue sodium and related fat deposition in adults with impaired lymphatic clearance. We found evidence of lymph stasis and tissue salt deposition that

correlated with local subcutaneous adipose tissue volume²⁴. Here, we will use noninvasive MRI to test whether similar lymphatic pathways are impaired in persons with SSSB, leading to tissue salt and fat storage, in comparison to the involvement of renal dysfunction in SSSB tissue profiles.

In addition to MRI, several external biophysical measurement tools exist to measure limb volume and tissue water content. These instruments include a bioimpedance spectrometer (LDex U400, Impedimed Limited) for measuring extracellular water content in the limbs, and a tissue dielectric probe (MoistureMeterD Compact, Delfin Technologies, Inc.) for measuring water content of the superficial dermis and adipose layers. These instruments aid in clinical diagnosis of other lymphatic disorders (the LDex is FDA approved to diagnose unilateral lymphedema of the arms or legs), which leads us to hypothesize that they may provide information on salt handling physiology if there is a lymphatic component to the disease. However, few studies have applied these devices in concert with MRI. We will apply these devices to study body composition related to SSSB and determine their potential use in screening of the phenotype.

2.0 Rationale and Specific Aims

The following hypotheses and specific aims were designed in response to a recent call from the American Heart Association (AHA) for i) standardized biomarkers to enable the clinical diagnosis of SSSB and ii) improved understanding of human tissue salt storage mechanisms²⁵.

Hypothesis 1: Tissue sodium content is elevated in adults predisposed for SSSB; tissue sodium and adiposity provide biomarkers for SSSB. **Aim 1:** Black adults without hypertension (20 male; 20 female) with BMI range=18 to 40 kg/m² and age range=18-55 years will be assessed for SSSB according to recent guidelines²⁶, and scanned using MRI to quantify tissue sodium and fat fraction in the lower extremities. Multivariable analyses will be applied to quantify relationships between tissue sodium, fat fraction as a surrogate of BMI, age, and sex with SSSB status. **Impact.** Unique tissue sodium and fat profiles may provide internal, mechanistic biomarkers of SSSB that could be used as endpoints in clinical trials of SSSB.

Hypothesis 2: Tissue sodium content is elevated in tissues affected by impaired lymphatic flow in adults with SSSB. **Aim 2:** The same participants will be scanned using noninvasive MR lymphangiography to quantify lymphatic flow velocity in the lower extremities. Non-parametric tests will be applied to evaluate the association between lymphatic flow and tissue sodium content in adults evaluated for SSSB. **Impact.** Identifying the extent of lymphatic dysfunction in SSSB could motivate novel treatment strategies to improve lymphatic pumping and tissue sodium clearance.

Hypothesis 3: Elevated tissue sodium content is associated with reduced renal perfusion in adults with SSSB. **Aim 3:** The same participants will be imaged using noninvasive MR spin-labeling techniques to measure kidney perfusion (ml blood/100g

tissue/min). Non-parametric tests will be applied to evaluate the association between kidney perfusion and peripheral tissue sodium content in adults evaluated for SSBP. Impact. Imaging of renal cortical circulation, where sodium-filtering nephrons are located, related to tissue sodium stores in SSBP may have potential to portend salt sensitive hypertension.

The overall goal of this work is to provide noninvasive imaging tools to assess a more complete spectrum of mechanisms underlying SSBP, which will motivate the use of these tools in future clinical trials to evaluate risk of SSBP or therapies to modify tissue sodium storage.

Study procedures will evaluate healthy and obese normotensive black adults using a set of already tested non-invasive MRI techniques developed at Vanderbilt University Institute of Imaging Science (VUIIS) and biophysical instruments available at the VUMC (IRB #103172, #160199). Participants will also be assessed for SSBP using current standard practices for measuring changes in blood pressure after periods of high salt diet and low salt diet through the Clinical Research Center following IRB-approved protocols developed by collaborator [name] (IRB #151943).

3.0 Inclusion/Exclusion Criteria

Inclusion criteria will include identification as black race, age between 18 and 55 years, and BMI between 25 and 40 kg/m². Additionally, subjects must be normotensive or pre-hypertensive adults who are willing to adhere to study diets and who are able to provide informed consent.

The following exclusion criteria will apply:

- Prevalent cardiovascular disease or use of medications for cardiovascular disease
- Current or prior history of hypertension or use of blood pressure lowering medications
- Current or prior history of diabetes mellitus or use of anti-diabetic medications
- Prevalent renal disease (eGFR < 60 ml/min/1.73m²), abnormal serum sodium or potassium
- Current or prior smoker
- Current pregnancy
- Current steroid use
- Contraindications to MRI
- Persons who are deemed clinically unsuitable for an MRI by their treating physician and/or VUIIS MRI technologist
- Severe claustrophobia
- Open wounds on the top of the feet or hands or at locations of interest for measurement of bioimpedance and tissue dielectric.

Also excluded are subjects incapable of giving informed written consent:

- Subjects who are non-English speaking
- Subjects who cannot adhere to the experimental protocols for any reason, or have an inability to communicate with the researcher.
- Subjects who have limited mental ability to give informed consent, mentally retarded, altered mental status, mental disability, confusion, or psychiatric disorders.
- Prisoners

4.0 Enrollment/Randomization

We will enroll 20 black adults (10 female and 10 male) who meet the inclusion and exclusion criteria. To analyze study hypotheses, and for comparison to normal weight individuals, we will share data from the study cohort of [name] (IRB #151943).

The following recruitment approaches will be used: Vanderbilt CTSA (VICTR) Research Notification Distribution List, the linked email system which reaches Vanderbilt faculty and staff, as well as members of the Middle Tennessee community, and ResearchMatch, a national online registry maintained at Vanderbilt which allows people to self-register and express interest as research participants. Additional patients may be recruited from external sites. IRB approved flyers/advertisements of the study may be distributed in the public local to Vanderbilt and surrounding areas as additional means of subject recruitment for this study. The SUBJECT LOCATOR program is part of a toolset available through VICTR that enables teams to specify inclusion/exclusion criteria for a specific study. The inclusion/exclusion criteria are codified for computable use and combined with data coming through VU Clinical Systems to proactively identify individuals who might qualify for a study. Once a 'match' is made, research study personnel are alerted using confidential messaging or a secure web portal and they may then use the information to further review the subject's information using the Vanderbilt Electronic Medical Record. If the subject is further deemed a candidate for the study, the study personnel will notify the subject's care provider who will then ask the subject if they would be interested in communicating with study personnel.

At the screening visit, history study consent will be obtained, a medical and physical examination administered, and protocol eligibility determined. If a subject meets inclusion criteria, without any exclusion criteria, the subject will be enrolled. Subjects will receive serial low- and high-salt diets in a randomized crossover design. The randomization (using permuted blocks) will occur to one of two dietary sequences: (1) high-salt, washout, then low-salt diet, or (2) low-salt, washout, then high-salt diet. Randomization assignment will occur at screening and before baseline to ensure sufficient time to prepare the subjects' provided meals.

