All low-salt meals will be provided to participant by the study. Subjects will pick up the prepared meals, snacks, and sodium free water at the CRC at times and intervals most convenient to the participant. The low-salt diet will include a maximum of 600mg (26 mEq) of sodium per day. Subjects are encouraged to consume all food as provided and expected to have no substitutions or additions. The calorie needs for weight maintenance will be assessed at screening. The low salt meal plan contains 2500-2800 calories. This calorie level is sufficient for the majority of the research population. Additional low-salt snacks will be added as need should the subject require additional calories. The high-salt diet supplies will consist of the subject's "usual" diet, supplemented with 2 bouillon broth packets each day, which will be provided by the study personnel. Each broth packet contains 48 mEq sodium for a total of approximately 100 mEq additional sodium intake per day. This method conveniently raises total salt intake to >200mEq/day (> 4,600 mg sodium/day) in over 95% of healthy volunteers obviating the need for additional prepared meals and visits.

Subjects, while on the low- and high-salt phases of the diet, will receive calcium supplementation. Calcium will be supplied by 2 antacid tablets taken by mouth; each will provide 750 mg of calcium.

Diet 1 visit

The same protocol as the baseline visit (described above) will be followed, with the exception that the subject will not undergo MRI. Other study procedures, including return of the 24-hour urine collection, blood pressure, and heart rate measures, obtaining venous blood draw in the supine position will be identical to the baseline visit. The biophysical exam may be performed while subjects are laying supine. After this Diet 1 visit, the subject will enter a minimum seven-day washout period. This will consist of the subject adhering to their "usual" diet. They will be given their 24-hour urine collection kit, to be completed before the "washout" visit.

Washout visit

The same protocol as the baseline visit will be followed, except that subjects will not undergo MRI. After this washout visit, the subject will crossover to the opposite salt diet from week 1. They will also be given their 24-hour urine collection kit.

Diet 2 visit

Protocol Version: 5
Protocol Date: 07/27/2020

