9.0 Statistical Considerations

Subjects who are overweight or obese (n=20) will be recruited through this IRB. To analyze study hypotheses, and for comparison to normal weight individuals, we will share data from the study cohort of [name] (IRB #151943). This will include identical data acquired from at least n=20 subjects who are normal weight (18 to <25 kg/m²) and who meet identical inclusion/exclusion criteria.

Statistical analysis procedures for Aim 1: Statistical analyses will be performed by key study personnel and members of the Center for Quantitative Sciences at the VUMC. The primary statistical objective of Aim 1 is to test the hypothesis that adults who are salt sensitive have higher baseline tissue sodium relative to adults who are not salt sensitive. To test this, we will divide participants into those who are salt sensitive (SS, ≥5 mmHg change in mean arterial pressure ΔMAP following high salt diet compared to low salt diet) or not salt sensitive (NSS, <5 mmHg ΔMAP), according to a review of methods and recommendations from Kurtz et al.²⁶. The metric ΔMAP represents a continuous variable of SSBP. A Mann Whitney U test will be applied to determine whether tissue sodium content is significantly different in SS and NSS groups. Based on a prior study of tissue sodium storage in adults who are hypertensive (n=10)

or normotensive (n=12)¹⁹ we anticipate a similar difference in tissue sodium of 6±4 (mean ± standard deviation, mmol/L) between SS and NSS adults. Our study is designed to provide at least 80% power to detect differences in tissue sodium with a two-sided significance of p<0.05.

Our secondary statistical objective of Aim 1 is to test the hypothesis that tissue sodium content and potential risk factors for SSBP, including biological sex, age, and tissue fat/water fraction as a sensitive surrogate of BMI, are related to Δ MAP as a continuous variable. We will apply multivariable regression analysis using tissue sodium, fat/water fraction, biological sex, and age as independent variables, and Δ MAP as the dependent variable among all participants. With a sample size of 40 , we should be able to evaluate the four predictors of Δ MAP (each with one degree of freedom) without over-fitting the model.

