6.3 Randomization and Blinding

All subjects will undergo the same interventions. However, the order of the study interventions will be randomized using a randomized crossover design.

This is not a blinded study.

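### Diet sequence is randomised but enters no analysis, so any drift in blood pressure between periods goes uncorrected into individual ΔMAP; the cost is precision and power.

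*Protocol*

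**What the plan says.** **Design.** Protocol section 4.0 allocates diet order at random: "Subjects will receive serial low- and high-salt diets in a randomized crossover design". It adds: "The randomization (using permuted blocks) will occur to one of two dietary sequences", namely "1) high-salt, washout, then low-salt diet, or (2) low-salt, washout, then high-salt diet". SAP section 6.3 agrees that "the order of the study interventions will be randomized using a randomized crossover design" and attaches no analysis to it. Between the diets, "the subject will enter a minimum seven-day washout period" (protocol section 5.0).

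**Outcome and label.** Protocol section 9.0 classes a participant as "salt sensitive (SS, ≥5 mmHg change in mean arterial pressure ΔMAP following high salt diet compared to low salt diet"; everyone else is not salt sensitive. One cutoff serves both sequences. SAP section 6.1 defines ΔBP as low-salt minus high-salt pressure, the opposite sign, also with no period term.

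**Analyses.**
- Aim 1 primary: a two-group comparison of tissue sodium. The SAP adds sex.
- Aim 1 secondary, protocol: "We will apply multivariable regression analysis using tissue sodium, fat/water fraction, biological sex, and age as independent variables", with ΔMAP as the outcome. The SAP version drops age.
- Aims 2 and 3, protocol: regression of tissue sodium on flow velocity (Aim 3: renal perfusion, by similar methods), continuous ΔMAP, sex and age.
- Aims 2 and 3, SAP: correlations by salt-sensitivity group, and interaction models with sex and fat/water fraction as covariates.
- SAP section 9: a general ANOVA on an undefined treatment group, adjusted for centre and surgical category. SAP section 9.1 is still template text.

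None of these names sequence or period.

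**The concern.** A two-period crossover randomises order so that a change over time can be separated from the diet effect. Averaged over balanced sequences, drift cancels. This study, however, does not mainly estimate an average diet effect: it uses each person's own ΔMAP, as the outcome of the Aim 1 secondary model, as a predictor in the protocol's Aims 2 and 3, and to form the Aim 1 groups. Drift does not cancel within a person. With about 40 participants, avoidable noise in ΔMAP, or labels that depend partly on which diet came first, could weaken associations the study hopes to find.

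**Working it through.** **The plan's own figure.** SAP section 6.1 claims at least 80% power with 20 per group, a difference of 6 mmol/L, SD 4 and two-sided 0.05. Normal approximation: 6 / (4 × √(2/20)) − 1.96 = 4.74 − 1.96 = 2.78, so power is 99.7%. The claim holds as a lower bound and is not disputed. It assumes labels without error.

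**Algebra.** Let S be the true high-minus-low response and π the drift in MAP from period 1 to period 2.
- Low-salt first: ΔMAP = S + π, so the effective cutoff on S is 5 − π.
- High-salt first: ΔMAP = S − π, so the effective cutoff on S is 5 + π.

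The SAP's reversed sign changes the direction, not the size.

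**Size.** Assumptions, not in the documents: S normal with mean 4 and SD 5 mmHg; sequences 1:1 (the ratio is not stated); π of 0 to 3 mmHg. The true share at or above 5 is 1 − Φ(0.2) = 42.1%. The share labelled salt sensitive is 1 − Φ((1 − π)/5) with low-salt first and 1 − Φ((1 + π)/5) with high-salt first. The mislabelled share is the average absolute distance of these from 42.1%. The variance ratio is (25 + π²)/25, and the fractional loss in correlation is 1 − 1/√ratio.

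| π (mmHg) | Labelled SS, low first | Labelled SS, high first | Mislabelled | Variance ratio | Loss in correlation |
|---|---|---|---|---|---|
| 0 | 42% | 42% | 0% | 1.00 | 0% |
| 1 | 50% | 34% | 8% | 1.04 | 2% |
| 2 | 58% | 27% | 15% | 1.16 | 7% |
| 3 | 66% | 21% | 22% | 1.36 | 14% |

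The assumed mean puts 42% in the salt-sensitive group. If instead 74% are salt sensitive (the protocol's background figure for black adults) with the same SD, mislabelling is 6%, 13% and 19%.

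**Sequence as a covariate in the ΔMAP regression.** Simulated with N=40, four predictors, SD 5 and an assumed correlation of 0.45 between sodium and true ΔMAP. With no drift, power is 82% without sequence and 81% with it; at π=2, 75% and 81%. Another simulated setting gave 83% and 81% with no drift, and 73% and 80% at 2 mmHg. The covariate costs about 1 to 2 points if it was not needed.

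**Relabelling with period-adjusted ΔMAP.** The estimate of π is half the between-sequence difference in mean ΔMAP, with standard error SD/√N: 5/√40 = 0.8 mmHg, or 5/√20 = 1.1 mmHg if sequence is known only for the 20 enrolled here. This error itself mislabels people. Simulated Mann-Whitney power (mean 4, SD 5, N=40, a 6 mmol/L step at the true label, SD 4):

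| π (mmHg) | Planned label | Adjusted label |
|---|---|---|
| 0 | 99% | 95% |
| 0.5 | 97% | 95% |
| 1 | 93% | 95% |
| 2 | about 76% | 95% |

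With no drift, adjustment mislabels about 5% of people who would otherwise all be labelled correctly. At 74% salt sensitive and no drift it cuts power from 96% to about 88%.

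**False positives.** With no true sodium difference, π=3, SD 6 and 50% salt sensitive, the simulated type I error is 4.9%. If an assumed 2 mmol/L effect of the last diet remains in tissue sodium at the MRI, it is 8.4%, returning to 4.9% after period adjustment.

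**The case against.** The strongest reply is that no drift is shown. The documents report no period effect, and the design limits the obvious mechanism. Diet 1 is the third visit, and the baseline visit already uses the full procedure of an hour supine and averaged cuff readings, so much habituation may precede both ΔMAP readings. The SAP's target days for them are only 7 and 21. This stands: the sizes above are an assumed range, and below about 1 mmHg the effect is small.

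The cost objections also stand. Adjusting the label loses power when there is no drift. The protocol justifies four predictors at N=40, so a fifth needs a sentence of support. At least 20 participants come from another cohort; section 9.0 promises identical data from it but does not list sequence.

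A reader might infer several stronger things that the documents do not support:
- *That drift creates false findings.* With balanced sequences and sodium unrelated to sequence, it does not. The exception needs sodium to depend on the last diet. Protocol section 5.0 allows the MRI before the diets or at least a week after diet 2, and SAP sections 6.4 and 6.5 place it at day 28 or later, at least 7 days off study diet. Whether any residue remains is unknown.
- *That every analysis rests on the label.* ΔMAP is the outcome only in the Aim 1 secondary model, and the protocol's Aims 2 and 3 use it as a continuous variable.
- *That the SAP's general ANOVA already covers this.* Treatment group is undefined there; even read as sequence, it would correct neither the label nor the Aim 1 to 3 models.

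**Conclusion.** The gap is real: a randomised design factor is left out of every specified analysis. Its consequence is conditional. Under the assumed mean 4 and SD 5 mmHg, a drift of 1 to 3 mmHg mislabels about 8% to 22% of participants and weakens correlations by 2% to 14%; zero drift does no harm. The base-case loss is precision and power. False-positive risk arises only if an effect of the last diet also persists in tissue sodium measured after diet 2. Adjusting the continuous models is cheap enough to prespecify without evidence of drift. Replacing the primary split with an adjusted one is not justified, because it pays only when drift is well above 1 mmHg.

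**What to change.** **Change in the SAP (and protocol section 9.0):**
1. Add randomised sequence as one covariate to the regressions that use continuous ΔMAP or ΔBP: Aim 1 secondary, and Aims 2 and 3 as the protocol specifies them.
2. Report the estimated period effect with its confidence interval, and the counts of salt-sensitive and other participants by sequence.
3. Keep the planned 5 mmHg split as primary. Repeat it as a sensitivity analysis with period-adjusted ΔMAP: subtract the estimated π in the low-first sequence and add it in the high-first sequence.
4. Request the sequence variable for the shared cohort now, and state what will be done if it is unavailable.

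**Cost.** One degree of freedom in a model justified for four predictors at N=40 (about 1 to 2 points of power with no drift); a data request to the shared cohort; and, in the sensitivity analysis only, some added label error if there is no drift (Mann-Whitney power about 99% to 95% in the assumed scenario). No visit or procedure changes. Carryover cannot be fully separated from period in a two-sequence, two-period design, and the SAP should say so.
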